Pupil measurement	X	X				X		X		X	
Slit-lamp biomicroscopy	X	X	X	X	X	X	X	X	X	X	X
Corneal staining	X	X	X	X	X	X	X	X	X	X	X
IOP check (8:00 a.m.)	X	X	X	X	X	X	X	X	X	X	X
Gonioscopy	X	X		X		X	X	X	X	X	
Pachymetry (contact)	X	X				X		X		X	
Specular microscopy (non-contact)	X ¹	X				X		X			X^1
Visual field	X									X	
Anterior segment OCT	X	X		X		X		X		X	
IOP diurnal curve		X^2						X^2			
Dilated fundus exam	X	X				X		X		X	

Procedure	Screening V1 Day -35 to -28	Baseline V2 -7 to -1 Days	Randomization/ Treatment V3 Day 1	Treatment V4 Day 3 +/- 1 day	Treatment V5 Day 7 +/- 1 day	Treatment V6 Day 14 +/- 1 day	Treatment V7 Day 21 +/- 1 day	Treatment V8 Day 25 +/- 1 day	Surgery V9 Day 28	Follow- up V10 Day 33- 38	Follow- up V11 Day 42- 49
Physical exam	X	X								X	
Vitals	X	X								X	
Lab tests	X	X^3				X^3				X^3	
Pregnancy test	X	X	X							X	
Study drug administration			X								
Cataract surgery									X		
Aqueous humor collection									X		
Implant recovery									X		
Dispense TRAVATAN Z			X								
Collect TRAVATAN Z								X			
Receive pre-surgical medications								X			
Dismiss patient, complete exit form											X

Non-contact specular microscopy can be performed anytime during the site visit.

IOP will be measured at 8 a.m., 10 a.m., and 4 p.m. for the diurnal curve endpoint.

Blood draws will be conducted prior to the daily administration of the TRAVATAN Z into the non-study eye. Samples collected as Visits 6 and 10 will additionally be used to determine the systemic exposure to travoprost as described in Sections 15.1.7 and 1.6.

ENV515-01 PHASE 2A CLINICAL STUDY, COHORT 2

Cohort 2 Protocol Synopsis

Investigational Product: ENV515-3 (Travoprost) Intracameral Implant

Phase: 2a

Study Objective:

• Evaluate the long-term safety, tolerability, efficacy, and systemic exposure to travoprost following a unilateral, single dose of two ENV515-3 (travoprost) intracameral implants in the study eye in patients with bilateral ocular hypertension or primary open-angle glaucoma

Clinical Hypotheses:

- A single dose of ENV515-3 (travoprost) Intracameral Implant is numerically comparable to timolol maleate 0.5% ophthalmic solution dosed twice daily in the control of IOP over 12 months in patients with bilateral ocular hypertension or primary open-angle glaucoma
- ENV515-3 (travoprost) Intracameral Implant has an acceptable safety profile

Study Design:

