- 21. Patients who, per investigator's judgment, are not good clinical trial candidates due to personal (e.g., perceived willingness or ability to comply with protocol, significant traveling distance to medical center) and/or medical (e.g., mental illness, other non-ocular medical conditions, or laboratory abnormalities that might negatively impact trial participation or outcome) conditions that would likely impede the patient's successful study completion or planned analyses.

Response Measures:

Primary Efficacy Measure:

• Change from baseline in time-matched IOP measurements at Week 2, Week 6, and Week 12 (Day 14, 42, and 84) for study and non-study eye

Secondary Efficacy Measures:

- Change from baseline and percent change from baseline in time-matched IOP measurements for study eye and non-study at all other study time points and visits
- Difference in change from baseline and percent change from baseline in time-controlled IOP measurements between study eye and non-study eye at all study time points and visits
- Cumulative % of study and non-study eyes with at least 20, 25, and 30% reduction in IOP at all study time points and visits
- Cumulative % of patients with IOP <18 at all time points at each study visit
- Mean IOP at all visits all time points

Safety Measures: Assessed by evaluating changes from baseline in the following:

- Specular microscopy (non-contact)
- Slit-lamp biomicroscopy
- Corneal staining
- Dilated fundus examination
- Gonioscopy exam
- Anterior chamber OCT exam
- Pupil measurement
- Pachymetry (contact)
- BCVA
- Visual Field

- Body system assessment
- Vital signs
- Non fasting clinical laboratory tests (chemistry, hematology, and urinalysis)
- Urine pregnancy tests for females of childbearing potential
- AEs

Pharmacokinetic Measures:

• Systemic exposure to travoprost via analysis of travoprost acid in plasma

Study Extension 1 Synopsis, Table 3.

Confidential

Table 2: Time and Events Schedule, Cohort 2

Note: V16/Month 12 Time and Events Schedule should only be used if patients are not continuing into the Cohort 2 Study Extension 1 and plan to exit the study at V16/Month 12. If the patient is continuing into the Cohort 2 Study Extension 1, V16/Month 12 should follow the Time and Events Schedule in the Cohort 2

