- During Screening (Visit 1) and Dosing (Visit 3), only one IOP timepoint in the morning is needed (see Section 12 for specific time window).
- During Day 2 (Visit 4) and Day 28 (Visit 5a), only the 8 a.m. IOP timepoint is needed. Day 14 (Visits 5) and Day 42 (Visit 6) require full diurnal evaluation.
- Lab and PK samples were not collected at Day 2 (Visit 4) and Day 28 (Visit 5a). Pregnancy test is only required at Day 14 (Visit 5).
- Timolol maleate 0.5% ophthalmic solution is given to the patient to take their first dose in the non-study eye the evening of the their Day 1 Dosing (Visit 3) then dose BID for the remaining portion of the study. Patients will be instructed to return their used bottle(s) at each visit for accountability purposes. A new supply of timolol maleate 0.5% ophthalmic solution will be provided on a monthly basis starting at Day 42 (Visit 6) through Month 11 (Visit 15). During post dose study visits, ensure Timolol maleate 0.5% ophthalmic solution is administered after the 8 AM IOP measurement.
- ⁷ Gonioscopy photographs are not collected at Day 2 (Visit 4).
- V16/Month 12 Time and Events Schedule should only be used if patients are not continuing into the Cohort 2 Study Extension 1 and plan to exit the study at V16/Month 12. If the patient is continuing into the Cohort 2 Study Extension 1, V16/Month 12 should follow the Time and Events Schedule in the Cohort 2 Study Extension 1 Synopsis, Table 3.

Specular microscopy is needed for all study eyes on all indicated visits; for non-study eyes, it is collected only during Screening (Visit 1) and Exit/Early Exit (Visit 16). Additional measurements may be taken at the investigator's discretion.

ENV515-01 PHASE 2A CLINICAL STUDY, COHORT 2 EXTENSION 1

Cohort 2 Extension 1 Protocol Synopsis

Investigational Product: ENV515-3 (Travoprost) Intracameral Implant

Phase: 2a Cohort 2 Extension 1

Cohort 2 Study Extension 1 Objective:

• Extend the ENV515-01 Ph2a Cohort 2 study duration beyond 12 months by an additional 6 months to continue evaluation of the ENV515-3 long term safety, efficacy, and biodissolution in patients with bilateral ocular hypertension or primary open-angle glaucoma

Clinical Hypotheses:

 A single dose of two ENV515-3 (travoprost) Intracameral Implants will demonstrate end of duration of IOP treatment effect and full biodissolution in the time period between 13 and 18 months

Cohort 2 Study Extension 1 Design:

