2. PROTOCOL SUMMARY

ENV515-01 is a multicenter, open-label, prospective, active-comparator-controlled Phase 2a study of ENV515 (travoprost) Intracameral Implant comprising three stages:

- The completed Cohort 1 was a 28-day study focused on evaluation of the initial safety, efficacy, and pharmacokinetic properties of ENV515 conducted in glaucoma patients scheduled for cataract removal during which the ENV515 implant is removed during the cataract procedure 28 days after implantation. This cohort was covered in a separate SAP and no further mention of this cohort will be made in this SAP.
- Cohort 2 is a 12-month study with a 6-month optional Extension 1 followed by an additional 3-month optional Extension 2 (for a total of up to 21 months) that is focused on evaluation of the long-term safety and efficacy in glaucoma patients during which the two ENV515-3 implants are followed through their biodissolution while the duration of intraocular pressure (IOP)-lowering efficacy is assessed.
- Cohort 3 is a 12-month study with a 6-month optional Extension 1 followed by an additional 6-month optional Extension 2 (for a total of up to 24 months) that is focused on evaluation of the long-term safety in glaucoma patients during which one or two ENV515-3-2 implants per study eye are followed through their biodissolution.

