4. ANALYSIS POPULATIONS

The safety population will be defined as any patient receiving at least one dose of study medication in the study. The safety population will be used for all analyses.

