8. EFFICACY EVALUATION

8.1 Primary Efficacy Analysis

The primary efficacy endpoint for this study is the change from baseline in time-matched IOP measurements for the study and non-study eye. Intraocular pressure is collected at 8 am. Values for IOP and change from baseline will be summarized by visit and time, cohort dose group, and eye as specified in Section 3. Baseline will be defined as the last IOP measurement prior to implantation and will be time-matched. No formal statistical testing will be done.

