10. CHANGES TO THE ANALYSES PLANNED IN THE PROTOCOL

This analysis plan is for an abbreviated CSR. Therefore, the primary endpoint will be summarized, but no formal statistical testing will be done. There will be no summaries for secondary endpoints. The planned summaries in the protocol for changes in corneal thickness, VA, endothelial cell count and morphology, slit lamp biomicroscopy exam findings, binocular indirect ophthalmoscopy, visual field assessment, anterior segment photos, and pupil measurement will not be created. These data will instead be available in listings.

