11. LIST OF PLANNED TABLES

Rho Table Identifier	Table No.	Title	Population
DS-TAA	14.1.1	Disposition	Safety
DM-TAA	14.1.2	Demographics	Safety
EF-TAA	14.2.1	Summary of Intraocular Pressure by Visit and Time Point	Safety
AE-TAA	14.3.1.1	Summary of Adverse Events	Safety
AE-TAB	14.3.1.2	Summary of Adverse Events by System Organ Class and Preferred Term	Safety
AE-TAC	14.3.1.3	Summary of Ocular Adverse Events by System Organ Class and Preferred Term	Safety
AE-TAD	14.3.1.4	Summary of Related Adverse Events	Safety
AE-TAE	14.3.1.5	Summary of Severe Adverse Events	Safety
AE-TAF	14.3.1.6	Summary of Serious Adverse Events	Safety
LB-TAA	14.3.2.1	Summary of Chemistry by Visit	Safety
LB-TAB	14.3.2.2	Summary of Hematology by Visit	Safety
LB-TAC	14.3.2.3	Summary of Urinalysis by Visit	Safety
VS-TAA	14.3.3.1	Summary of Vital Signs by Visit	Safety
VA-TAA	14.3.4.1	Summary of Visual Acuity	Safety
EX-TAA	14.3.5.1	Summary of Exposure	Safety

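### The only IOP table for Cohorts 2 and 3 pools readings before and after rescue drops, and no table counts rescue, so later study-eye means can hide loss of ENV515 effect

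*SAP*

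**What the plan says.** The SAP for Cohorts 2 and 3 (21 January 2019) plans a single efficacy output. Section 8.1 states: "Values for IOP and change from baseline will be summarized by visit and time, cohort dose group, and eye". Section 11 lists it as Table 14.2.1, "Summary of Intraocular Pressure by Visit and Time Point". Section 4 adds that "The safety population will be used for all analyses", and section 10 that "the primary endpoint will be summarized, but no formal statistical testing will be done"; summaries of secondary endpoints are dropped.

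Rescue appears nowhere in that SAP: there is no flag, no count, no listing of its own and no rule for readings taken after it. Protocol section 18 has no such rule either.

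The protocol does expect rescue. Under 11.6, a Cohort 2 study eye may receive four weeks of AZOPT and, if control fails, timolol to the end of the study. A Cohort 3 study eye goes straight to timolol to the end of the study. Either eye may also be rescued at any time at the investigator's discretion. Having been rescued is one of the four conditions that must all hold for early exit (11.8).

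Duration of effect is a stated question for Cohort 2. SAP section 2 says its implants are followed "while the duration of intraocular pressure (IOP)-lowering efficacy is assessed". The Cohort 2 synopsis hypothesizes that a single dose "is numerically comparable to timolol maleate 0.5% ophthalmic solution dosed twice daily in the control of IOP over 12 months", and the Extension 1 synopsis that the implants "will demonstrate end of duration of IOP treatment effect and full biodissolution in the time period between 13 and 18 months".

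**The concern.** A rescued study eye stays in the safety population and keeps supplying readings to Table 14.2.1. Those readings reflect whatever the implant still does plus the drops. The later the visit, the more eyes may be in that state, and the table shows no sign of it. Some rescued eyes may instead leave early under 11.8, which also changes who makes up the late means.

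Two quite different histories can therefore give similar rows. In one, the implants are still working; in the other, some have failed and drops have taken over. Telling these apart is what the Cohort 2 hypotheses ask for, and the abbreviated report has no other efficacy table that could do it. The planned exposure table does not help, because it counts days to dissolution or removal of the implant and not days to loss of effect.

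**Working it through.** The plan gives no figure on this point, so there is none to reproduce.

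**1. Inputs**

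- Group sizes: Cohort 2 n=5 (SAP 2.2); Cohort 3 low dose n=6 and high dose n=9 (Protocol 10.4).
- Illustrative effect of a working implant: -5.1 mmHg, the Cohort 1 result for 28.2 µg at Day 25, n=7 (Protocol 1.4.2).
- Added lowering from rescue drops: not in the documents; assumed 3 to 6 mmHg.

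**2. Shift per rescued eye** = added lowering / n

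| Group | n | Drops add 3 mmHg | Drops add 6 mmHg |
|---|---|---|---|
| Cohort 2 | 5 | 3/5 = 0.60 | 6/5 = 1.20 |
| Cohort 3 low dose | 6 | 3/6 = 0.50 | 6/6 = 1.00 |
| Cohort 3 high dose | 9 | 3/9 = 0.33 | 6/9 = 0.67 |

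**3. Example, Cohort 2.** Suppose working implants give -5.1 mmHg, a failed implant gives 0, and the failed eye is on drops.

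- One failed eye. Implant effect alone: (4 × -5.1 + 0)/5 = -4.08. Planned table: (4 × -5.1 - 3)/5 = -4.68, up to (4 × -5.1 - 6)/5 = -5.28.
- Two failed eyes. Implant effect alone: (3 × -5.1)/5 = -3.06. Planned table: (3 × -5.1 - 6)/5 = -4.26, up to (3 × -5.1 - 12)/5 = -5.46.

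At the upper end the table reads better than if every implant were still working (-5.1).

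**4. Does leaving out post-rescue readings recover the implant effect?** No. With one failed eye removed, the other four average -5.1. That is further from -4.08 than the pooled -4.68 when drops add 3 mmHg, and closer than the pooled -5.28 when they add 6. Eyes not yet rescued are a selected group, so neither mean isolates the implant.

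**5. Can Cohort 2 Day 84, a primary visit, be affected?** Both versions of the rule need two visits after Day 1 at least 4 weeks apart.

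- Day 14 to Day 42 is 28 days, so the rule can be met at Day 42. A strict four-week course then ends on Day 70, or Day 73 if that visit fell on Day 45. The earliest Day 84 visit is Day 77 (±7 days in Table 2 and 12.8). By this route Day 84 is off drops.
- 11.6 has control judged at the next study visit, and only then says to stop if IOP is controlled. If drops run on to that visit, Day 84 is on drops.
- Day 2 to a late Day 28 visit (Day 31) is 29 days. A course from Day 31 ends on Day 59. An unscheduled check two weeks later falls on Day 73 and can lead to permanent timolol before Day 77.
- Discretionary rescue can occur at any time.

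In Cohort 3 the rescue rule looks only at visits after Day 84, so only discretionary rescue could reach that visit.

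**6. What the listings would show.** SAP 5.4 and Listing 16.1.4 cover all concomitant medications, and Listing 16.2.1 covers IOP. Protocol 16.2.1 requires drug name, dose, route, duration with start and stop dates, frequency and indication. The eye is not among these fields, and timolol is also the comparator in every fellow eye.

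**The case against.** The case for leaving the plan alone has four parts.

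- **Rescue is not concealed.** AZOPT is not the comparator, so it would stand out in Listing 16.1.4 with dates and indication, and there are only 20 patients. This stands against any inference that the SAP hides who was rescued. It does not make the table readable: two listings have to be matched by hand, and for timolol the eye may not be identifiable.
- **The report is abbreviated.** The IND is being withdrawn (SAP 1), the stated objective for these cohorts is safety and tolerability (SAP 2.1), nothing is tested, and the cuts are declared in section 10. A summary of all readings is legitimate if labelled as such. That keeps the remedy small. It does not remove the need for a label, since this is the only efficacy table.
- **Some of what is needed is already planned.** SAP 3 reports the number of subjects in every continuous summary, and SAP 5.1 tabulates discontinuations and reasons. This is correct; only the rescue counts and their link to early exit are missing.
- **A pre-rescue-only mean may be no nearer the truth.** Step 4 confirms this, so that mean cannot be offered as the corrected estimate.

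A reader might also infer that the Cohort 2 Day 84 result is contaminated. The documents do not support that: a strict four-week course begun at Day 42 is over before the Day 84 window opens, and the other routes are possible but not shown to have occurred. Nor does the conflict over the rescue trigger leave post-rescue readings undefined. An eye is rescued when drops start, whichever trigger applied.

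**Conclusion.** The concern holds and should be fixed. As written, section 8.1 and Table 14.2.1 pool readings from before and after rescue, and no planned table counts or flags rescue. Later study-eye means can therefore hide loss of ENV515 effect. The issue is mainly for Cohort 2. The Cohort 3 synopsis lists no efficacy measure, although its IOP goes into the same table.

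The size is 0.6 to 1.2 mmHg per rescued eye in Cohort 2, and 0.5 to 1.0 (low dose) or 0.3 to 0.7 (high dose) in Cohort 3. This rests on an assumed 3 to 6 mmHg added by the drops. The number rescued is not in the documents, so no total shift can be given. Nor is the direction of error between eyes fixed, because fellow eyes may also be rescued. For Cohort 2 Day 84 the supported statement is that it could be affected, not that it is.

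**What to change.** All changes are descriptive.

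1. Add to Table 14.2.1, by visit and eye, the number rescued to date and the number who left early after rescue.
2. Add a short listing of each rescue: patient, eye, drug, start and stop dates, and days from implantation. Take the eye from source data where it was not recorded. Present this as supportive evidence on duration of effect.
3. Flag post-rescue readings and show the IOP summary with and without them. Count readings at the visit where rescue starts as pre-rescue (Protocol Table 5, footnote 9, implies this for Cohort 3). State how readings after a temporary AZOPT course are classed. Note under the table that neither mean isolates the implant effect.
4. Reconcile the Cohort 2 rescue passages. The synopsis uses a change of less than 20% as the trigger, while 11.6 uses investigator opinion. Section 11.6 also permits up to two rescue treatments and then concludes that only one AZOPT treatment is possible.

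The cost is some SAP wording, a few count rows, one listing and a second version of one table for 20 patients. A source-data check may be needed to establish which eye received timolol as rescue. Late cells without post-rescue readings will be very small and should be read with that in mind.

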9. SAFETY EVALUATION

9.1 Overview of Safety Analysis Methods

Adverse events, clinical laboratory results, vital signs, and physical exam findings will be tabulated at the subject level. All other safety measurements will be made at the eye level. Unless otherwise noted, baseline will be defined as the last measurement prior to receiving the implant.

9.2 Extent of Exposure

The number of days from implant insertion to implant dissolution or removal will be summarized descriptive statistics. All other exposure data will be available in subject listings. Exposure will be calculated only for the study eye. No exposure information for the TRAVATAN Z eye will be collected.

9.3 Adverse Events

Adverse events will be coded using the Medical Dictionary for Regulatory Activities (MedDRA) version 18.0 and categorized by system organ class using preferred terms. Events will be tabulated overall and by ocular/non-ocular status. Treatment related adverse events and severe adverse event will also be summarized. Serious adverse events will be summarized.

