Category	Group 1 (low dose) (n=7) n (%)	Group 2 (high dose) (n=10) n (%)	Group 3 (low dose) (n=2) n (%)	Group 4 (high dose) (n=2) n (%)	All Groups (non- study eye) (n=21) n (%)
At least 1 ocular AE	4 (57)	7 (70)	2 (100)	2 (100)	7 (33)
At least 1 ocular AE unresolved by last visit	0	2 (20)	0	0	0
At least 1 early ocular AE (Day 1-7)	4 (57)	7 (70)	2 (100)	2 (100)	3 (14)
At least 1 late ocular AE (Day 19-25)	0	1 (10)	1 (50)	0	2 (10)

Table 11: Classification of Adverse Events Occurring in > 1 Patient

	ENV515-3		ENV515-1		TRAVATAN Z
Preferred Term	Group 1 (low dose) (n=7) n (%)	Group 2 (high dose) (n=10) n (%)	Group 3 (low dose) (n=2) n (%)	Group 4 (high dose) (n=2) n (%)	All Groups (non-study eye) (n=21) n (%)
Ocular hyperemia	4 (57)	4 (40)	2 (100)	1 (50)	4 (19)
Foreign body sensation in eyes	1 (14)	3 (30)	2 (100)	1 (50)	0
Punctate keratitis	3 (43)	1 (10)	2 (100)	1 (50)	1 (5)
Anterior chamber cell	1 (14)	2 (20)	0	1 (50)	0

	ENV	515-3	ENV515-1		TRAVATAN Z	
Conjunctival haemorrhage	1 (14)	3 (30)	0	0	1 (5)	
Lacrimation increased	0	3 (30)	1 (50)	0	0	
Iritis	0	2 (20)	0	1 (50)	0	
Photophobia	0	2 (20)	0	1 (50)	1 (5)	
Posterior capsule opacification	0	2 (20)*	0	0	0	

^{*}Occurred after cataract removal and intraocular lens (IOL) implantation

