1.5. Interim Summary of Results from Cohort 2 of ENV515-01 Phase 2a Study

1.5.1. Summary of Disposition of Cohort 2 Patients in ENV515-01 Phase 2a Study Patient disposition is presented in Table 12. A total of five patients were enrolled into the study across two sites. All patients completed the study and there were no early discontinuations.

Table 12: Patient Disposition Table for Cohort 2 of ENV515-01 Phase 2a Study

	ENV515-3 (n=5)
Category	n (%)
Treated	5 (100)
Safety	5 (100)
Intent-to- treat	5 (100)
Per-protocol	4 (100)
Completed 3 months post dose	5 (100)
Discontinued	0 (0)

1.5.2. Interim Summary of Safety Results from Cohort 2 of ENV515-01 Phase 2a Study

There were no SAEs reported in Cohort 2 of the study. The ocular adverse events observed in the study were generally mild in nature and related to the injection procedure. (Table 13 and Table 14).

Table 13: Overall Summary of Ocular Adverse Events for ENV515-3 Excluding Hyperemia

Reported Events (summarized by preferred term)	ummarized by Subjects		Causality	Outcome
Foreign body sensation	4 (80)	3 -Mild1- Moderate	4 - Injection Procedure 1 - ENV515 Implant	Resolved
Endothelial cell count loss	2 (40)	Mild	ENV515 Implant	1 - Ongoing 1 - Resolved
Punctate keratitis	2 (40)	1 – Mild 1 - Moderate	1 - Injection Procedure 1 - Unrelated	Resolved
Blurred vision	2 (40)	Mild	1 - ENV515 Implant 1 - Unrelated	Resolved
Anterior chamber cell and flare	1 (20)	Mild	Injection Procedure	Resolved
Photophobia	1 (20)	Mild	Injection Procedure	Resolved
Iritis	1 (20)	Mild	Injection Procedure	Resolved
Corneal edema	orneal edema 1 (20)		ENV515 Implant	Resolved
Focal microcystic epithelial edema	1 (20)	Mild	ENV515 Implant	Resolved
Trichiatic eyelash	1 (20)	Mild	Unrelated	Resolved

		~	1		. •	1
Cc	m	t1	А	er	١tı	2

Ocular soreness	1 (20)	Moderate	Injection Procedure	Resolved
Eyelid edema	1 (20)	Mild	Injection Procedure	Resolved
Ocular discomfort	1 (20)	1 – Mild 1 - Moderate	Injection Procedure and Unrelated	Resolved
Worsening of visual field	1 (20)	Mild	Unrelated	Ongoing

Table 14: Summary of Hyperemia Adverse Events for ENV515-3 Dose Arm

Reported Adverse Events	Number of Incidences Reported	Study Eye or Both Eyes	Severity	Causality	Outcome
Ocular hyperemia	2	Study Eye	Severe	Injection Procedure	Resolved
Ocular hyperemia	2	Study Eye	Moderate	Injection Procedure	Resolved
Ocular hyperemia	1	Study Eye	Moderate	ENV515 Implant	Resolved

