9.3 Adverse Events

Adverse events (AEs) will be coded using the Medical Dictionary for Regulatory Activities (MedDRA) and categorized by system organ class using preferred terms by dose group. Events will be tabulated with respect to their intensity and relationship to the study drug. Only treatment-emergent AEs will be summarized. A treatmentemergent AE will be defined as any AE with onset date on or after the first exposure date. AEs will be tabulated separately for study eye, non-study eye and non-ophthalmic events.

All serious adverse events (SAEs) and other significant events, including withdrawals due to AEs, will be individually summarized in the CSR.

All treatment-emergent AE and SAE data will be presented in subject listings.

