3. GENERAL ANALYSIS AND REPORTING CONVENTIONS

The following is a list of general analysis and reporting conventions to be applied for this study.

- Categorical variables will be summarized using counts (n) and percentages (%) and will be presented in the form "n (xx.x)". To ensure completeness, summaries for categorical and discrete variables will include all categories, even if no subjects had a response in a particular category.
- Continuous variables will be summarized using mean, standard deviation (SD), minimum, maximum, median, and number of subjects. The mean and median will be reported to one more level of precision than the original observations, and the SD will be reported to 2 more levels of precision than the original observations. The minimum and maximum will be the same precision as the original data.
- All analyses will be performed using SAS® System version 9.4 or higher.
- Dates will be displayed as ddmmmyyyy (e.g., 24Jan2005).

Patient-level analyses will be presented with the following columns:

Cohort 2	Low Dose Cohort 3	High Dose Cohort 3
2 implants ENV515-3	1 implant ENV515-3-2	2 implants ENV515-3-2
(28.2 µg travoprost)	(26.1 μg travoprost)	(52.2 µg travoprost)

Eye-level analyses will be presented with the following columns:

Cohort 2		Low Dose Cohort 3		High Dose Cohort 3	
2 implants ENV515-3 (28.2 µg travoprost)		1 implant ENV515-3-2 (26.1 μg travoprost)		2 implants ENV515-3-2 (52.2 µg travoprost)	
ENV515-3 SE	Timolol maleate 0.5% NSE	ENV515-3 SE	Timolol maleate 0.5% NSE	ENV515-3 SE	Timolol maleate 0.5% NSE

Note: SE=study eye, NSE=non-study eye

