9.5.3 Visual Acuity (VA)

Visual acuity will be measured using the Early Treatment Diabetic Retinopathy Study (ETDRS) chart according to the manufacturer's specifications. The number of letters missed will be collected and summarized by cohort group and eye for each visit. Visual acuity data, including best corrected distance, will be presented in subject listings.

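### The Cohort 2/3 SAP counts ocular adverse events per subject under the three ENV515 doses, with no split between the implant eye and the timolol eye

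*SAP*

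**What the plan says.** The SAP dated 21 January 2019 covers Cohorts 2 and 3.

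- **Level of tabulation (Section 9.1).** "Adverse events, clinical laboratory results, vital signs, and physical exam findings will be tabulated at the subject level". All remaining safety measurements are placed at eye level.
- **Columns (Section 3).** The patient-level layout has three columns: Cohort 2, Cohort 3 low dose and Cohort 3 high dose. None is for timolol. A second layout, introduced by "Eye-level analyses will be presented with the following columns", has six: study eye and timolol non-study eye within each of the three groups.
- **Adverse events (Section 9.3).** "Events will be tabulated overall and by ocular/non-ocular status". Treatment-related, severe and serious events are also to be summarised. Related is not defined.
- **Tables (Section 11).** There is one ocular adverse event table, 14.3.1.3, and its title mentions no eye.

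Other outcomes in the same SAP keep the eye. For IOP (Section 8.1): "Values for IOP and change from baseline will be summarized by visit and time, cohort dose group, and eye as specified in Section 3". For visual acuity (Section 9.5.3): "The number of letters missed will be collected and summarized by cohort group and eye for each visit".

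The Cohort 1 SAP has the same subject-level sentence in its Section 9.1, but its Section 9.3 adds: "AEs will be tabulated separately for study eye, non-study eye and non-ophthalmic events".

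**The concern.** The design gives each patient a built-in comparator: the fellow eye, on timolol. For ocular events the natural question is how often they occurred in implant eyes and how often in timolol eyes. A per-subject count under a dose heading answers neither. It counts patients with an event in either eye and labels the result with the ENV515 dose.

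Safety and tolerability are the stated objective of these cohorts (SAP Section 2.1). SAP Section 10 moves corneal thickness, endothelial cell count, slit lamp findings, fundus examination, visual field and pupil measurement from summaries to listings. That leaves the adverse event tables as a main part of the tabulated ocular safety evidence. IOP and visual acuity are specified by eye; adverse events are not. (Section 10 also names visual acuity among the dropped summaries, but Section 11 keeps Table 14.3.4.1 for it.)

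**Working it through.** **1. What the text implies.** Section 9.1 puts adverse events at subject level and contrasts them with eye-level measurements. Section 3 gives subject-level tables three ENV515 columns. Section 9.3 adds only the ocular/non-ocular split, and Section 11 lists one ocular table. Together these place an ocular event in either eye under the patient's ENV515 dose.

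**2. Contrast with Cohort 1.** The Cohort 1 SAP starts from the same Section 9.1 sentence and then splits by eye in its Section 9.3. Protocol Table 10, which reports Cohort 1, gives the fellow eye its own column, headed "All Groups (non- study eye) (n=21) n". The 2019 SAP has the starting sentence without the addition.

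**3. Shift per affected patient.** If a patient's only ocular event is in the timolol eye, the displayed rate exceeds the implant-eye rate by 1/n. Group sizes are from SAP Section 2.2 (Cohort 2) and Protocol Section 10.4 (Cohort 3).

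| Group | n | 1/n, percentage points |
|---|---|---|
| Cohort 2 | 5 | 20.0 |
| Cohort 3, low dose | 6 | 16.7 |
| Cohort 3, high dose | 9 | 11.1 |

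**4. How many such patients?** The documents do not say. The interim Cohort 2 tables in Protocol Section 1.5.2 give partial evidence.

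- *Hyperemia (Table 14).* Incidences: 2 + 2 + 1 + 10 + 1 = 16. Study eye: 2 + 2 + 1 + 8 + 1 = 14. Both eyes: 2. Fellow eye only: 16 − 14 − 2 = 0.
- *Any ocular event (Table 13).* Foreign body sensation occurred in 4 of 5 patients, with causality given as "4 - Injection Procedure 1 - ENV515 Implant". Both are study-eye causes, so at least 4/5 = 80% of implant eyes had an ocular event. The per-subject figure cannot exceed 5/5 = 100%, so the any-ocular row for Cohort 2 can shift by at most 20.0 points.
- *Individual terms (Table 13).* No eye is given. Punctate keratitis and blurred vision are each 2/5 with one unrelated entry; trichiatic eyelash and worsening visual field are each 1/5 and unrelated. Depending on the eye, the implant-eye rate is 20% or 40% for the first two and 0% or 20% for the last two.

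The documents contain no Cohort 3 adverse event data.

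**5. The undefined term.** Protocol Section 17.1 gives Cohorts 2 and 3 five causality selections: unrelated, implant, comparator, injection procedure and other study procedure. In Table 14 the 16 incidences divide into 5 implant, 5 injection procedure and 6 unrelated. Counting implant only gives 5/16 = 31%; counting implant or injection gives 10/16 = 62.5%. These are incidences, not patients, so they show sensitivity to the definition and are not rates.

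**The case against.** **The layout is inferred.** No sentence assigns the three-column layout to adverse events, and the Cohort 1 SAP shows that subject-level counting can coexist with tables split by eye. This stands as far as it goes: the sponsor could produce eye-specific tables without contradicting Section 9.1. But in the Cohort 1 SAP an explicit sentence did that work, and here none does. A programmer following the 2019 text would have no instruction to split.

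**The effect may be nil.** The 20.0, 16.7 and 11.1 figures are simply 1/n, and no event confined to a timolol eye is documented. This stands. Nor do the interim tables rule such events out: both are titled for ENV515-3, so events in the fellow eye only may not appear in them.

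**Stronger readings that the documents do not support.** A reader might infer that the ENV515 ocular event rates will be materially inflated. That would require assuming that the unrelated events in Table 13 were in timolol eyes, and nothing says so. Cohort 1 rates cannot fill the gap, because that comparator was TRAVATAN Z over 28 days. A reader might also infer a departure from the protocol, but Protocol Section 18.1.2 does not require adverse events to be split by eye. Finally, a reader might think the protocol's suspected/not-suspected scale already keeps comparator events out of the related table. That scale refers to the investigational product, and Protocol Section 16.3 names timolol under that heading. The Cohort 2/3 selections are the ones that isolate the comparator.

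**The stakes are low.** The report is abbreviated because the IND is being withdrawn, nothing is formally tested, there are 20 patients, and adverse events are listed (Listing 16.3.1). This stands and sets the severity, although the SAP does not say that the listing shows the eye.

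**Conclusion.** The point holds and is minor. As written, the 2019 SAP leads to per-subject ocular adverse event counts under ENV515 dose headings. An event confined to the timolol eye is counted there, and the timolol-eye rate is not displayed. The shift is 20.0, 16.7 or 11.1 percentage points per affected patient, by group. The number of affected patients is unknown and may be zero; for the any-ocular row in Cohort 2 it is at most one of five.

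This rests on reading Sections 9.1 and 3 together, and on the Cohort 3 group sizes in Protocol Section 10.4. It is a weakness in how the main safety outcome is presented, and does not show that any reported rate is wrong. The missing definition of related is a smaller matter of detail alongside it.

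**What to change.** 1. In SAP Section 9.3, state that ocular adverse events are presented by eye. Use the six study-eye/non-study-eye columns already in Section 3 for Table 14.3.1.3 and for the ocular rows of the related, severe and serious tables (14.3.1.4 to 14.3.1.6). Count an event in both eyes once in each eye.
2. As a minor clarification in the same section, state which of the Cohort 2/3 causality selections in Protocol Section 17.1 count as treatment related, including how injection-procedure and comparator events are handled.

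The cost is a few lines of SAP text and extra columns in four tables, with no new patients or visits. The change assumes that the eye was recorded for every ocular event. The documents show this only for Cohort 2 hyperemia (Protocol Table 14), so it should be checked against the adverse event form first.
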